3.1.2. Adverse Events and Serious Adverse Events

AEs and SAEs will be categorized according to MedDRA terms and summarized by system organ class and preferred term at the participant level. The time period for actively eliciting and collecting AEs and SAEs for each participant begins from the time the participant provides informed consent through and including the visit occurring 1 month after the last dose. For reporting purposes, only events occurring following study intervention will be counted in the summary tables. Events occurring prior to study intervention administration will only be included in listings.

3.2. Secondary Endpoints

Blood will be collected before Dose 1 (Visit 1), approximately 1 month after Dose 1 (Visit 2), and approximately 1 month after Dose 2 (Visit 4) to assess immunogenicity. Pneumococcal IgG concentrations and OPA titers for the candidate serotype will be measured in sera collected at Visits 1, 2, and 4:

- Pneumococcal IgG concentrations 1 month after Dose 1 and 1 month after Dose 2.
- Participants with predefined IgG concentration (0.35 µg/mL) 1 month after Dose 1 and 1 month after Dose 2.
- Fold rises of pneumococcal IgG concentrations from before Dose 1 to 1 month after Dose 1 and from 1 month after Dose 1 to 1 month after Dose 2.
- Pneumococcal OPA titers 1 month after Dose 1 and 1 month after Dose 2.
- Fold rises of pneumococcal OPA titers from before Dose 1 to 1 month after Dose 1 and from 1 month after Dose 1 to 1 month after Dose 2.

IgG concentrations and OPA titers above the LLOQ are considered accurate and their quantitated values will be reported. Missing assay results will not be imputed. The handling of assay values below LLOQ is discussed in [Section 5.3](#).

3.3. Exploratory Endpoints

CCI

3.4. Baseline Variables

Baseline will be the measurement obtained prior to Dose 1.

3.4.1. Demographics and Medical History

The demographic variables are age at Dose 1 (in months), sex (male or female), race (Black/African American, American Indian or Alaska Native, Asian, Native Hawaiian or other Pacific Islander, White, multiracial, and not reported), and ethnicity (Hispanic/Latino, non-Hispanic/non-Latino, and not reported). In cases where more than 1 category is selected for race, the participant will be counted under the category “multiracial” for analysis.

Medical history will be categorized according to MedDRA.

3.4.2. Concomitant Vaccines and Concomitant Medications

The name and date of administration for all nonstudy vaccinations received from 28 days prior to Visit 1 through Visit 4, and medications taken to treat SAEs from the time of signing of the ICD through Visit 4, will be collected and recorded on the CRF.

Concomitant vaccines and concomitant medications will be coded using the WHODD.

3.5. Other Safety Endpoints

Primary safety endpoints are described above in the Primary Endpoints — Safety section ([Section 3.1](#)). This section describes supportive safety endpoints.

Supportive AE endpoints include related AEs, severe AEs, immediate AEs, and AEs leading to discontinuation. Immediate AEs are those occurring within the first 30 minutes after each dose. The time period for collecting all supportive AE endpoints begins from the time the participant provides informed consent through 1 month following the last dose. For reporting purposes, only events occurring following Dose 1 will be counted in the summary tables. Events occurring prior to Dose 1 will only be in listings.

4. ANALYSIS SETS (POPULATIONS FOR ANALYSIS)

Data for all participants will be assessed to determine if participants meet the criteria for inclusion in each analysis population prior to releasing the database for the first planned analysis, and classifications will be documented per standard operating procedures. The populations are defined below:

Participant Analysis Set	Description
Screened	All participants whose parents/legal guardian sign the ICD.
Randomized	All participants who are assigned a randomization number in the IRT system.
Dose 1 evaluable immunogenicity	
All participants who:
 
 1. are eligible and randomized, 2. receive the study intervention to which they are randomized, 3. have at least 1 valid immunogenicity result within 27 to 56 days, inclusive, after Dose 1, and 4. have no other major protocol deviations as determined by the clinician up to the 1-month post-Dose 1 visit. 
The Dose 1 evaluable immunogenicity population will be the primary analysis population for the immunogenicity results before Dose 1 and 1 month after Dose 1.
 
Participants will be grouped on a randomized basis.

Dose 2 evaluable immunogenicity	
All participants who:
 
 1. are eligible and randomized, 2. receive both doses of study intervention to which they are randomly assigned, 3. have at least 1 valid immunogenicity result within 27 to 56 days, inclusive, after Dose 2, and 4. have no other major protocol deviations as determined by the clinician. 
The Dose 2 evaluable immunogenicity population will be the primary analysis population for the immunogenicity results at 1 month after Dose 2.
 
Participants will be grouped as randomized.

miITT immunogenicity	
All randomized participants who receive at least 1 dose of the study intervention and have at least 1 valid immunogenicity result after study intervention administration.
 
Participants will be grouped as randomized.

Safety	
All participants who receive at least 1 dose of the study intervention.
 
Participants will be grouped as administered.

For the Dose 1 and Dose 2 evaluable immunogenicity population definitions, the blood collection window has been expanded by 1 extra day before, and 14 days after, the protocol-specified blood collection window of 28 to 42 days as defined in the protocol, for consistency with established rules in the 13vPnC and 20vPnC development programs.

For determination of the evaluable immunogenicity populations, items 1 through 3 above will be computerized checks of the data, while item 4 will be determined by clinical review. A major protocol deviation is a protocol deviation that, in the opinion of the sponsor's clinician, would materially affect assessment of immunogenicity, eg, participant receipt of a prohibited vaccine or medication that might affect immune response or a medication error with suspected decrease in potency of the vaccine. The sponsor's clinician will identify those participants with major protocol deviations before any analysis specified in [Section 7.2.1](#) is performed.

Reactogenicity results (local reactions and systemic events) after a specified dose will be reported for all participants in the safety population who have any e-diary data collected after the specified dose.

5. GENERAL METHODOLOGY AND CONVENTIONS

Methodology for summary and statistical analyses of the data collected in this study is described here. In general, the study data will be summarized by study intervention group. CIs for all endpoints in the statistical analysis will be presented as 2-sided at the 95% level.

For all immunogenicity endpoints, the analysis will be primarily based on the evaluable immunogenicity populations. An additional analysis will be performed based on the mITT population if there is a large enough difference (>10%) in the numbers of participants included between the mITT and the evaluable immunogenicity populations. Participants will be summarized according to the study intervention group to which they were randomized.

The safety analyses are based on the safety population. Participants will be summarized according to the study interventions they received.

5.1. Hypotheses and Decision Rules

There is no statistical hypothesis testing planned for this study. All statistical analyses are descriptive and for estimation purpose.

5.2. General Methods

5.2.1. Analysis for Binary Data

Descriptive statistics for categorical variables (eg, proportions) are the percentage (%), the numerator (n) and the denominator (N) used in the percentage calculation, and the 2-sided 95% CIs where applicable.

The exact 95% CI for binary endpoints for each group will be computed using the F distribution (Clopper-Pearson).¹

5.2.2. Analysis for Continuous Data

5.2.2.1. Descriptive Statistics

Unless otherwise stated, descriptive statistics for continuous variables are n, mean, median, standard deviation, minimum, and maximum.

5.2.2.2. Geometric Mean

The GM for each group will be calculated as the mean of the logarithmically transformed assay results and then exponentiating the mean. The 2-sided 95% CI will be obtained by exponentiating the limits of the CI for the mean of the logarithmically transformed assay results based on the t distribution.

5.2.2.3. Geometric Mean Fold Rise

Fold rise is the change in the assay results from an earlier time point to a later time point. The GMFR will be calculated as the mean of the difference of antibody levels (later time point - earlier time point) on the natural log scale and then exponentiating the results. The 2-sided 95% CIs will be obtained by exponentiating the limits of the CIs for the mean difference of the logarithmically transformed assay results based on the t distribution. Only data from participants with nonmissing assay results at both time points will be included in the GMFR calculation.

5.2.2.4. Reverse Cumulative Distribution Curves

Empirical RCDCs for immunogenicity results will be plotted as a step function of the proportion of participants with the assay results equal to or exceeding a specified value over the full range of the observed assay results.

5.3. Methods to Manage Missing Data

In evaluations, missing reactogenicity e-diary data will not be imputed. A partial AE start date (missing day, missing both month and day) will be imputed by assigning the earliest possible start date using all available information, such as the stop date of the AE and the administration date(s) from the same participant, following the Pfizer standard of handling incomplete AE start dates. A completely missing start date for an AE is not allowed in data collection. No other missing information will be imputed in the safety analysis.

Serology result values that are designated as serum QNS, IND, or “not done” will be set to missing. No imputation will be done for these missing values. Missing serology results will not be imputed. Assay results above the LLOQ will be reported, but results that are below the LLOQ, or BLQs, will be set to $0.5 \times \text{LLOQ}$.

The LLOQ and LOD (when applicable) for each assay will be provided by the laboratory performing the assays prior to any statistical analysis of assay results.

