#### **9.3.1.2. Analyses for Continuous Data**

Unless otherwise stated, descriptive statistics for continuous variables are n, mean, median, standard deviation, minimum, and maximum.

Assay results above the LLOQ will be reported, but results that are below the LLOQ, or BLQs, will be set to  $0.5 \times \text{LLOQ}$  in the calculation of GMCs and set to LLOQ in the analysis of fold rises.

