2.1. Modifications to the Analysis Plan Described in the Protocol

The exploratory endpoints, estimands, and corresponding analyses are specified in the SAP.

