6.2.3. Fold Rise in IgG Concentrations

- Estimand: GMFRs in IgG concentrations from Dose 1 to 1 month after Dose 1, and from 1 month after Dose 1 to 1 month after Dose 2 ([Section 3.2](#)).
- Analysis sets: Dose 1 evaluable immunogenicity population for GMFR from before Dose 1 to 1 month after Dose 1; Dose 2 evaluable immunogenicity population for GMFR from 1 month after Dose 1 to 1 month after Dose 2 ([Section 4](#)).
- Analysis time points: From Dose 1 to 1 month after Dose 1 and from 1 month after Dose 1 to 1 month after Dose 2.
- Analysis methodology: Descriptive statistics ([Section 5.2.2.3](#)).
- Reporting results: n, GMFRs, and the corresponding 2-sided 95% CIs will be presented for each group.

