6.2.5. Fold Rise in OPA Titers

- Estimand: GMFRs in OPA titers from Dose 1 to 1 month after Dose 1, and from 1 month after Dose 1 to 1 month after Dose 2 ([Section 3.2](#)).
- Analysis sets: Dose 1 evaluable immunogenicity population for GMFR from before Dose 1 to 1 month after Dose 1; Dose 2 evaluable immunogenicity population for GMFR from 1 month after Dose 1 to 1 month after Dose 2 ([Section 4](#)).
- Analysis time points: From Dose 1 to 1 month after Dose 1 and from 1 month after Dose 1 to 1 month after Dose 2.
- Analysis methodology: Descriptive statistics ([Section 5.2.2.3](#)).
- Reporting results: n, GMFRs, and the corresponding 2-sided 95% CIs will be presented for each group.

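### SAP 5.3 sets below-LLOQ results to half the LLOQ with no exception for the secondary IgG and OPA fold rises, the protocol sets them to the LLOQ there, and the change is neither declared nor explained

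*SAP*

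**What the plan says.** Protocol 9.3.1.2 separates two uses of a result below the LLOQ (BLQ). Such a result becomes half the LLOQ "in the calculation of GMCs and set to LLOQ in the analysis of fold rises".

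SAP 5.3 has a single rule, half the LLOQ, and does not distinguish GMCs from fold rises: "results that are below the LLOQ, or BLQs, will be set to $0.5 \times \text{LLOQ".

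The SAP's structure carries that rule to the fold rises:

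- SAP 3.2 lists the IgG and OPA fold rises among the secondary endpoints and then says: "The handling of assay values below LLOQ is discussed in" Section 5.3.
- SAP 5.2.2.3 defines the GMFR. Its only condition on the data is this: "Only data from participants with nonmissing assay results at both time points will be included in the GMFR calculation".
- SAP 6.2.3 ("GMFRs in IgG concentrations from Dose 1 to 1 month after Dose 1", and on to 1 month after Dose 2) and SAP 6.2.5 ("GMFRs in OPA titers from Dose 1 to 1 month after Dose 1", likewise) point to 5.2.2.3 and add no rule for low values.

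SAP 2.1 is the section for departures from the protocol's analysis plan. Its whole content is: "The exploratory endpoints, estimands, and corresponding analyses are specified in the SAP". The version 2 changes listed in SAP Table 1 do not mention low values or fold rises either.

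**The concern.** Two written rules apply to the same prespecified secondary estimands and give different numbers. Someone who knows the GMFR from the protocol would expect one value, and the SAP would produce another. Nothing in the SAP warns of this. Two programmers working from the two documents could report different GMFRs from the same data.

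The difference is unlikely to average out in the first interval, from before Dose 1 to 1 month after Dose 1. Protocol 4.2.2 expects participants to be naive to serotype 3 vaccination, so BLQ results are more likely before Dose 1 than after it. When they are, the SAP rule gives the larger GMFR.

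The study is descriptive, so these estimates are themselves the result. Protocol 9.5 says they are meant to support a decision on further development.

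**Working it through.** The plan gives no figure on this point, so there is nothing to reproduce. The check is algebra on the two rules.

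**Inputs**

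- BLQ value in fold rises: L (the LLOQ) in Protocol 9.3.1.2, L/2 in SAP 5.3.
- GMFR: the exponentiated mean, over participants with both results, of d = ln(later) − ln(earlier) (Protocol 9.3.1.4, SAP 5.2.2.3).
- Group size: 50 (Protocol 9.5). The values 45 and 40 pairs are assumptions that allow for exclusions.
- LLOQ and BLQ shares: not given. SAP 5.3 leaves the LLOQ to the laboratory. All shares below are assumptions.

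**Step 1: effect on one pair.** Replacing L by L/2 lowers a substituted log value by ln 2. Therefore:

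- BLQ at the earlier time only: d rises by ln 2.
- BLQ at the later time only: d falls by ln 2.
- BLQ at both times, or at neither: d is unchanged.

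**Step 2: effect on the GMFR.** Let a, b and c be the shares of pairs that are BLQ early only, late only and at both times. Then p_early = a + c and p_late = b + c, so a − b = p_early − p_late. The mean of d shifts by (p_early − p_late) × ln 2, which gives

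GMFR(SAP) / GMFR(protocol) = 2^(p_early − p_late).

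This is exact and does not depend on the LLOQ or on the distribution of the data.

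**Step 3: assumed net shares**

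| p_early − p_late | Factor |
|---|---|
| 0% | 1.00 |
| 10% | 2^0.10 = 1.07 |
| 25% | 2^0.25 = 1.19 |
| 50% | 2^0.50 = 1.41 |
| 75% | 2^0.75 = 1.68 |
| 90% | 2^0.90 = 1.87 |
| 100% | 2^1 = 2.00 |

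BLQ results at the later time reduce the factor. With p_late = 10%, p_early = 50% gives 2^0.40 = 1.32, and p_early = 90% gives 2^0.80 = 1.74.

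**Step 4: effect of one participant.** Each net pair that is BLQ early multiplies the GMFR by 2^(1/50) = 1.0140 with 50 pairs, 2^(1/45) = 1.0155 with 45, and 2^(1/40) = 1.0175 with 40.

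**Step 5: numerical check.** In simulated log-normal data with 49.9% BLQ before and 0.4% after, the GMFR was 11.54 under half the LLOQ and 8.19 under the LLOQ. The ratio is 1.41, and the formula gives 2^(0.499 − 0.004) = 1.41. The shares are illustrative and confirm the algebra only.

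**Step 6: intervals and arms.** The confidence limits are computed from the same log differences, so they change too. The ratio of the candidate GMFR to the control GMFR is multiplied by 2^(net share in candidate − net share in control).

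**The case against.** The strongest case on the other side has five parts.

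- **SAP 5.3 never mentions fold rises.** Protocol 9 says the SAP gives further detail, and SAP 2.1 declares no change, so 5.3 could be an incomplete restatement that leaves the protocol's fold-rise rule in force. This reading is possible. The reference from SAP 3.2 makes it the less natural one, and it would still leave two rules for one estimand.
- **The change is permitted.** Protocol 9 lets the SAP modify the analysis and requires an amendment only for major changes to the primary endpoints or their analyses. That stands. Nor is SAP 2.1 a complete register, since the wider blood-draw window is not listed there. But SAP 4 states that window beside the rule and gives a reason ("for consistency with established rules in the 13vPnC and 20vPnC development programs"). The BLQ change has neither a statement nor a reason anywhere.
- **No decision is shown to turn on it.** No hypothesis test and no between-arm GMFR analysis is planned. For the first interval, randomisation makes the baseline BLQ shares equal in expectation, so the inflation falls on both arms alike unless the shares differ by chance or after dosing. This limits the harm to an informal comparison of the arms. It does not correct the GMFR in either arm. For the second interval the earlier sample is itself post-randomisation, so the argument does not carry over.
- **The size is unknown.** This stands. Vaccine naivety does not guarantee BLQ baselines, and Protocol 4.2.2 also says that carriage peaks in this age group, so natural antibody is possible.
- **Half the LLOQ is a coherent choice.** With one rule throughout, each GMFR equals the ratio of the two GMCs on the same pairs. That is a good reason to keep it, and a good reason to say so.

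**Conclusion.** The point holds. The protocol and the SAP give different rules for BLQ results in the IgG and OPA fold rises, and the SAP neither declares nor explains the difference. The defect is the undeclared change. The change itself is allowed, and neither rule is claimed to be better.

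The two GMFRs differ by exactly 2^(p_early − p_late). The range runs from no difference, when BLQ shares are equal at the two times, to a doubling, when every pair is BLQ early and none late. The value in this trial cannot be computed from the documents.

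The scope is limited. The safety endpoints, the sample size and the percentage reaching the predefined IgG level do not depend on the fold-rise rule. IgG GMCs use half the LLOQ in both documents. The protocol sentence does not name OPA GMTs, so it sets up no conflict there. This should be fixed, but it does not threaten the primary objective.

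**What to change.** State one BLQ rule for fold rises in SAP 5.2.2.3 and 5.3, in either of two ways:

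- restore the protocol's rule, the LLOQ, for fold rises; or
- keep half the LLOQ, and declare it with a reason in SAP 2.1 or beside the rule, as SAP 4 does for the blood-draw window.

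In either case, report the GMFRs under the other rule as a sensitivity analysis, and tabulate the number and percentage of BLQ results by arm, assay and time point. The table lets a reader see how much the choice matters.

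The cost is one or two sentences in the SAP, one extra derivation and one small table. The sentences alone cure the undeclared departure. No new data and no change to trial conduct are needed.

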6. ANALYSES AND SUMMARIES

6.1. Primary Endpoints

6.1.1. Local Reactions and Systemic Events

6.1.1.1. Main Analysis

- Estimands:
 - The percentages of participants reporting local reactions (pain at the injection site, redness, and swelling) within 7 days after each dose ([Section 3.1.1](#)).
 - The percentages of participants reporting systemic events (fever, decreased appetite, drowsiness/increased sleep, and irritability) within 7 days after each dose ([Section 3.1.1](#)).
- Analysis set: Safety population with any e-diary data reported after each dose ([Section 4](#)).
- Analysis time point: Day 1 through Day 7 after each dose.
- Analysis methodology: Descriptive summary statistics ([Section 5.2.1](#)).
- Reporting results: The numerator (n) and denominator (N, defined as the number of participants who received the specific dose in the safety population and had any e-diary data reported after the specific dose) used for the calculation of the percentages. The percentages, and the associated 2-sided Clopper-Pearson 95% CI will be presented, by group and severity, for the following variable:
 - Maximum severity of each and any local reaction or systemic event on any day (Day 1 through Day 7) after each dose.

6.1.1.2. Supplementary Analyses

As supplementary analyses to support the assessment of local reactions or systemic events, the following endpoints (as defined in [Section 3.1.1](#)) may be summarized (provided data are not sparse) with the same analysis time point and analysis population:

- Duration (days) of each local reaction or systemic event after each dose.
- Onset day of each local reaction or systemic event after each dose.

These continuous endpoints will be summarized by displaying the n, mean, median, standard deviation, minimum, and maximum for each group.

Descriptive summary statistics for use of antipyretic/pain medication after each dose (see [Section 3.1.1](#)) will be provided for each group: n, N, percentage, and 2-sided 95% CI.

Figures

Bar charts with the percentages of participants for each local reaction or systemic event on each and any day (Day 1 through Day 7) after each dose will be plotted for each vaccine group, with different patterns displayed in the bar charts for different severity levels (each day) and different maximum severity levels (any day), respectively.

6.1.1.3. Sensitivity Analysis

Summary of local reactions and systemic events by maximum severity is also assessed using the e-diary and unplanned assessment data only.

6.1.2. Adverse Events

6.1.2.1. Main Analysis

- Estimand: The percentages of participants reporting AEs (excluding reactogenicity events collected on the AE CRF that are included in the local reaction or systemic event summary) from Dose 1 through 1 month after Dose 2 ([Section 3.1.2](#)).
- Analysis set: Safety population ([Section 4](#)).
- Analysis time point: Dose 1 through 1 month after Dose 2.
- Analysis methodology: Descriptive summary statistics ([Section 5.2.1](#)).
- Reporting results: The numerator (n) and the denominator (N) used in the percentage calculation, the percentage (%), and the corresponding 2-sided 95% Clopper-Pearson CI for participants reporting any AE, by system organ class and preferred term, will be presented for each group.

